1 LIST OF ABBREVIATIONS AND DEFINITIONS OF TERMS

Abbreviation	Definition
AE	Adverse event
ALT	Alanine transaminase
AST	Aspartate transaminase
BUN	Blood urea nitrogen
BMI	Body-mass index
CRF	Case report form
CRO	Clinical research organization
DSMB	Data and safety monitoring board
EIA	Enzyme immunoassay
FDA	Food and Drug Administration
GRAS	Generally regarded as safe
GDH	Glutamate dehydrogenase
GCP	Good clinical practice
HIPAA	Health Insurance Portability and Accountability Act
HMO	Human milk oligosaccharide
ID	Identification number
IEC	Independent ethics committee
IP	Investigational product
ISDA	Infectious Disease Society of America
IRB	Institutional review board
ICH	International Conference on Harmonization
NDA	Investigational New Drug
LDH	Lactate dehydrogenase
LNnT	Lacto-N-neotetraose
NGS	Next-generation sequencing
NAAT	Nucleic acid amplification tests
OTU	Operational taxonomic unit
OTC	Over the counter

Statistical Analysis Plan
Prolacta Bioscience Protocol 20-CT-001

Abbreviation	Definition
PO	Per os
RTF	Ready-to-feed
SAE	Serious adverse event
SHEA	Society of Hospital Epidemiologists of America
VRE	Vancomycin-resistant Enterococci

2 SCOPE OF THE STATISTICAL ANALYSIS PLAN

This version of the Statistical Analysis Plan (SAP) will focus on the safety analyses described in the protocol. These analyses will be included in an initial abbreviated safety report. The details of the analysis of primary and secondary endpoints are included here but will be expanded upon in an amended SAP for the full clinical study report.

3 INTRODUCTION

3.1 PREFACE

Human milk oligosaccharide (HMO) have recently become the objects of scientific inquiry. These complex sugars are extremely heat stable and are therefore found intact in donor milk and human milk-based products following pasteurization as well as in untreated mother's own milk.^{1,2,4} Approximately 200 different HMO structures have been identified, although any particular mother will only produce a subset of those. Studies have shown that HMOs can alter the gut microbiome by favoring the growth of certain organisms as well as, perhaps, by inhibiting others.⁴ It has also been demonstrated that HMOs can act as "decoy" receptors for a variety of pathogens and toxins.⁴ They have also been shown, *in vitro*, to directly interact with certain components of the adaptive immune system.⁴

As a result of the aforementioned activities, it is reasonable to expect that these molecules may be useful as therapeutic agents or medical foods. This is particularly the case in medical settings where the HMOs themselves or their metabolites may provide missing nutrients or other metabolic products for the dietary management of diseases where the microbiome plays a role, either in whole or in part. Examples might include conditions as disparate as inflammatory bowel disease and stem cell transplantation.

We hypothesize that *B. longum* subspecies *infantis* (*B. infantis*) might be a particularly beneficial organism to expand in the microbiome when managing such diseases in combination with HMOs. In infants, co-administration of *B. infantis* with human milk (via breast feeding) results in expansion of *B. infantis*, reduction in other potentially deleterious species, notably members of the Family

Statistical Analysis Plan

Prolacta Bioscience Protocol 20-CT-001

Enterobacteriaceae, and acidification of baby's stool through the production of certain short chain fatty acids.⁷ These dietary effects are postulated to be due to metabolism of HMOs by *B. infantis*, as infants receiving human milk in the absence of *B. infantis* don't show these effects. Importantly, *B. infantis* is not observed as a constituent of the human adult gut microbiota so it may therefore be necessary to administer both HMOs and *B. infantis* to obtain the full beneficial impact of HMOs feeding in adults.

Prolacta Bioscience manufactures human milk-based products from donated breast milk. In the course of the manufacture of human milk-based human milk fortifier, skim breast milk is ultra-filtered in order to concentrate proteins. Investigation of the permeate produced through this process demonstrated that human milk oligosaccharides were present in amounts comparable to those found in raw breast milk. Moreover, as the starting material consists of breast milk pooled from between 100 and 200 mothers, the full range of HMOs could be found. Subsequently, a method was developed to allow for the production of material with elevated concentrations of HMOs which contains little to no residual lactose through the introduction of lactase which is then removed.

An unconcentrated, pasteurized form of HMO material containing a proportional amount of lactose has already been used in an NIH sponsored clinical trial in premature infants with no reported ill effects.^v Prolacta Bioscience has also completed a healthy volunteer study using the same HMO material as in this trial (with no addition of *B. infantis*) which showed good tolerability. No treatment emergent adverse effects were reported over the course of the trial.⁶

The *B. infantis* preparation being used in this trial is a dietary supplement commercially available in the United States and marketed for use in infants. *B. infantis* is characterized as "generally regarded as safe" (GRAS).⁸

3.1 THE PURPOSE OF THE ANALYSES

The primary goal of this study is to evaluate the synergy of PBCLN-005 in varying doses with a fixed dose of *B. infantis*, compared with either component of the IP given alone. Synergy is defined as the enhanced gastrointestinal colonization of *B. infantis* upon feeding with HMO feeding. Secondary endpoints will measure changes in the gut microbiome, fecal metabolome and the subject's immune status as measured by systemic markers. We hypothesize that the combination will result in greater proliferation of *B. infantis* than was seen with the HMO concentrate alone.

Another objective is to understand the role of the low pH of the stomach in colonization of *B. infantis*. For most non-spore forming gut bacteria, the stomach is a barrier to colonization since acid exposure can reduce bacterial titer by 1,000- to 1,000,000-fold. While most subjects in the study will take an over-the-counter proton pump inhibitor (PPI; Zegerid: omeprazole plus sodium bicarbonate) to transiently reduce the production of gastric acid prior to *B. infantis* ingestion, one study group will ingest *B. infantis* without PPI pretreatment. We hypothesize that PPI pretreatment is necessary to observe *B. infantis* colonization.

Statistical Analysis Plan

Prolacta Bioscience Protocol 20-CT-001

We also hypothesize that ingestion of PBCLN-005 along with the *B. infantis* will result in a more marked change in immune markers than was seen in the previous study in healthy adults. We will, therefore, evaluate changes in circulating cytokine and growth factor levels following the ingestion of the study compared to baseline levels and between dose groups.

3.2 STUDY ENDPOINTS

3.2.1 Primary

The primary endpoint will be changes in the level of *B. infantis* from baseline evaluated by quantitative PCR using primers for species and strain. Quantitation limits will be demonstrated by qualification assays demonstrating the lower limit of detection, in order to establish minimum log-fold change in *B. infantis*, as it is expected that adult subjects will not harbor *B. infantis* in baseline samples.

3.2.2 Secondary

- Changes in stool microbiota will be measured as well as dynamic changes in the gut community structure. These changes will be evaluated by next generation sequencing using proportions of key bacterial operational taxonomy units (OTUs), relative abundance of various taxa, diversity (alpha and beta) and stability of communities and functional metabolomic changes.
- Changes in viability of proteobacteria and Enterococcus will be determined by plating on selective media. These measurements will *be* predictive for success in suppressing pathogenic bacterial relatives in future trials.
- Blood parameters, such as cytokine levels at study days -1, 8, 15 and 2 except for Cohort 5 who will also be evaluated on days 36, 43 and 57
- Determination of the need for protection of *B. infantis* from stomach acid in order for engraftment of the organism into the gut microbiome to occur.

3.2.3 Safety

- Total exposure to the test product will be calculated.
- Adverse events will be summarized by severity and relationship to study product.
- The laboratory evaluations listed below will be evaluated for clinical lab and medical safety at the following visits: Screening, Day 1, Day 15, Day 29, and, for Cohort 5, Day 43 and 57.
 - CBC with differential and platelets

- Alkaline phosphatase, alanine transaminase (ALT), aspartate transaminase (AST), lactate dehydrogenase (LDH), total and conjugated bilirubin, albumin and total protein for liver function
- Electrolytes (Na, K, Cl, and HCO₃)
- Glucose, total calcium, magnesium, phosphate, creatinine, and blood urea nitrogen (BUN) for renal function.
- Vital signs (heart rate, respiratory rate, temperature, and blood press are collected at the following visits: Screening, Day 1, Day 8, Day 15, Day 29, and for Cohort 5, Day 36, Day 43, and Day 57.
 - Heart rate
 - Respiratory rate
 - Temperature
 - Blood pressure

4 STUDY METHODS

4.1 STUDY DESIGN

The study is an unblinded six cohort multi-dose trial using 10 subjects per cohort for a total of 60 healthy adult volunteers ages 18-75 in order to evaluate the effects of the use of HMO Concentrate (PBCLN-005) and *B. infantis* on the human microbiome.

Six separate cohorts of both male and female study subjects will receive some form of the IP. In Cohort 1, the IP will consist of the standard dose of *B. infantis* alone. In cohort two, the IP will consist of only the PBCLN-005. In Cohort groups 3, 4, 5, and 6, the IP will consist of varying dose levels of PBCLN-005 together with *B. infantis*, with each cohort getting a single dose level of HMO. In Cohort groups 3, 4, 5, and 6, the IP will contain a standard dose of *B. infantis*.

Table 1 below summarizes the cohort dosing.

Table 1 Dosing cohorts

Cohort	Target HMO Amount (days 1-14)	PPI (days 1-7)	B. infantis (days 1-7)
1	None	Yes, 20 mg	Yes, one sachet
2	18g	Yes, 20 mg	None
3	4.5g	Yes, 20 mg	Yes, one sachet
4	9g	Yes, 20 mg	Yes, one sachet
5A	18g	Yes, 20 mg	Yes, one sachet
6	18g	No	Yes, one sachet

4.2 INCLUSION/EXCLUSION CRITERIA AND THE GENERAL PATIENT POPULATION

4.2.1 Inclusion Criteria

- Healthy adults between the ages of 18-75 years
- Willingness to complete study specific questionnaires
- Willingness to complete journal to record IP dosing times
- Willingness to complete all study procedures and clinic visits, and provide required samples
- Able to provide stool samples on specific study days
- Willingness to collect and process stool samples at home and transport stool samples to clinic
- Bristol Stool Score of 1 through 5 at time of screening
- Able to store up to 9 days of IP in refrigerator
- Sexually active females of child-bearing potential must agree to use highly effective methods of contraception during heterosexual intercourse throughout the study period and for three days following discontinuation of PBCLN-005, whichever comes later. Examples of highly effective methods include the use of two forms of contraception with one being an effective barrier method (e.g., a condom and spermicide used together), or have a vasectomised partner. Abstinence is acceptable as a life-style choice. Female subjects who utilize hormonal contraceptives as one of their birth control methods must have used the same method for at least 3 months before study dosing
- Provides informed consent

4.2.2 Exclusion Criteria

- Women who are pregnant or breastfeeding, or intend to become pregnant during the course of this study
- Subjects with allergy to, or other reason for contraindication of the PPI chosen for this study.
- Subjects with history of lactose intolerance
- Subjects who are on a PPI regimen
- Subject who has taken a probiotic during the previous 30 days, or intends to take a probiotic during the study
- Subject who has taken antibiotics within 120 days
- Alcohol or drug abuse during the last 12 months, including passing a screen for drugs of abuse at screening
- Unstable medical condition, in the opinion of the investigator
- Clinically significant abnormal laboratory test results at screening
- Subjects who are unable or unwilling to provide stool samples on a regular basis

- Participation in a clinical research trial within 30 days prior to screening
- Unable to give informed consent
- Any condition which may preclude subject's ability to comply with and complete the study or may pose a risk to the health of the subject.
- Carriage of *B. infantis* prior to study start, as determined by qPCR of stool
- Bristol Stool Score of 6 or 7 at time of screening

4.3 RANDOMIZATION AND BLINDING

The study will not utilize randomization or blinding.

Statistical Analysis Plan**Prolacta Bioscience Protocol 20-CT-001****4.4 SCHEDULE OF EVENTS**

The tables below give the schedule of events for each cohort.

Schedule of Events Table
Cohort 1

Protocol Number 20-CT-001																		
Schedule of Events For Cohort 1 (Day 0 through Day 29)																		
Events	Cohort 1 Screening	Cohort 1 Dosing Days															Cohort 1 Washout	
	D0 (≤ 90 days prior to D1)	D1	D2	D3	D4	D5 (+1D)	D6	D7	D8 (+2D)	D9	D10	D11	D12	D13	D14	D15 (+2D)	D22 (+2D)	D29 (+2D)
Clinic visit	X	X							X							X		X
Final Visit																		X
Informed consent	X																	
Review IE Criteria	X	X																
Medical History	X																	
Physical Exam	X																	X
Demographics (age, gender, ethnicity and race)	X																	
Vital Signs (Temp, BP, pulse, RR)	X	X							X							X		X
Height, weight and BMI	X																	
Prior & Con Meds	X	X							X							X		X
AEs		X							X							X		X

Statistical Analysis Plan

Prolacta Bioscience Protocol 20-CT-001

Cohort 1 (Cont.)

Protocol Number 20-CT-001																			
Schedule of Events For Cohort 1 (Day 0 through Day 29)																			
Events	Cohort 1 Screening	Cohort 1 Dosing Days																Cohort 1 Washout	
	D0 (≤ 90 days prior to D1)	D1	D2	D3	D4	D5 (+1D)	D6	D7	D8 (+2D)	D9	D10	D11	D12	D13	D14	D15 (+2D)	D22 (+2D)	D29 (+2D)	
Randomization		X																	
Dispense IP: B. infantis (≥8x10 ⁷ cfu/d) and aqueous dilute		X																	
Dosing: B. infantis (≥8x10 ⁷ cfu/d)		X	X	X	X	X	X	X											
Assess IP and Stool compliance										X								X	
Stool Questionnaires		X	X	X	X	X	X	X	X	X	X	X	X	X	X	X	X	X	
Daily Dosing and Flavor Questionnaire		X	X	X	X	X	X	X											
Patient Phone Calls			X	X	X	X	X	X											

Statistical Analysis Plan

Prolacta Bioscience Protocol 20-CT-001

Cohort 1 (Cont.)

Protocol Number 20-CT-001																		
Schedule of Events For Cohort 1 (Day 0 through Day 29)																		
Events	Cohort 1 Screening	Cohort 1 Dosing Days															Cohort 1 Washout	
	D0 (≤ 90 days prior to D1)	D1	D2	D3	D4	D5 (+1D)	D6	D7	D8 (+2D)	D9	D10	D11	D12	D13	D14	D15 (+2D)	D22 (+2D)	D29 (+2D)
Urine Drug Screen Test	X																	
Urine Pregnancy Test (Females of child-bearing potential)	X																	
Hematology & Chemistry testing	X	X														X		X
Immunology testing (Screening samples will not be evaluated for eligibility)	X	X							X							X		X
Stool (metagenomics) (Screening samples will not be evaluated for eligibility)	X	X				X			X							X	X	X
Stool (metabolomics) (Screening samples will not be evaluated for eligibility)	X	X							X							X		X
Stool (microbiology)	X	X							X							X		X
Fecal pH (using nitrazine paper)	X	X							X							X		X

Statistical Analysis Plan**Prolacta Bioscience Protocol 20-CT-001**

Schedule of Events Table
Cohorts 2, 3, 4, and 6

Protocol Number 20-CT-001

Schedule of Events For Cohorts 2, 3, 4, & 6 (Day 0 through Day 29)

Events	Cohorts 2, 3, 4, & 6 Screening	Cohorts 2, 3, 4, & 6 Dosing Days														Cohorts 2, 3, 4, & 6 Washout		
	D0 (≤ 90 days prior to D1)	D1	D2	D3	D4	D5 (+1D)	D6	D7	D8 (+2D)	D9	D10	D11	D12	D13	D14	D15 (+2D)	D22 (+2D)	D29 (+2D)
Clinic visit	X	X							X							X		X
Final Visit																		X
Informed consent	X																	
Review IE Criteria	X	X																
Medical History	X																	
Physical Exam	X																	X
Demographics (age, gender, ethnicity and race)	X																	
Vital Signs (Temp, BP, pulse, RR)	X	X							X							X		X
Height, weight and BMI	X																	
Prior & Con Meds	X	X							X							X		X
AEs		X							X							X		X

Statistical Analysis Plan

Prolacta Bioscience Protocol 20-CT-001

Cohorts 2, 3, 4, and 6 (cont.)

Protocol Number 20-CT-001																		
Schedule of Events For Cohorts 2, 3, 4 & 6 (Day 0 through Day 29)																		
Events	Cohorts 2, 3, 4, & 6 Screening	Cohorts 2, 3, 4, & 6 Dosing Days															Cohorts 2, 3, 4, & 6 Washout	
	D0 (≤ 90 days prior to D1)	D1	D2	D3	D4	D5 (+1D)	D6	D7	D8 (+2D)	D9	D10	D11	D12	D13	D14	D15 (+2D)	D22 (+2D)	D29 (+2D)
Randomization		X																
Dispense IP; B. infantis ($\geq 8 \times 10^7$ cfu/d) (except Cohort 2) (Note: On D1 dispense 9-day supply of PBCLN-005. On D8 dispense 5-day supply of PBCLN-005)		X							X									
Dosing: B. infantis ($\geq 8 \times 10^7$ cfu/d) (All Cohorts except Cohort 2)		X	X	X	X	X	X	X										
Dosing: PBCLN-005 1 bottle po bid (Target 4.5g, 9g or 18g)		X	X	X	X	X	X	X	X	X	X	X	X	X	X			
Assess IP and Stool compliance		X								X							X	X
Stool Questionnaire		X	X	X	X	X	X	X	X	X	X	X	X	X	X	X	X	X
Daily Dosing and Flavor Questionnaire		X	X	X	X	X	X	X	X	X	X	X	X	X	X			
Patient Phone Calls		X	X	X	X	X	X	X	X	X	X	X	X	X	X			

Statistical Analysis Plan

Prolacta Bioscience Protocol 20-CT-001

Cohorts 2, 3, 4 & 6 (cont.)

Protocol Number 20-CT-001																		
Schedule of Events For Cohorts 2, 3, 4, & 6 (Day 0 through Day 29)																		
Events	Cohorts 2, 3, 4, & 6 Screening	Cohorts 2, 3, 4, & 6 Dosing Days															Cohorts 2, 3, 4, & 6 Washout	
	D0 (≤ 90 days prior to D1)	D1	D2	D3	D4	D5 (+1D)	D6	D7	D8 (+2D)	D9	D10	D11	D12	D13	D14	D15 (+2D)	D22 (+2D)	D29 (+2D)
Urine Drug Screen Test	X																	
Urine Pregnancy Test (Females of child-bearing potential)	X																	
Hematology & Chemistry testing	X	X															X	X
Immunology testing (Screening samples will not be evaluated for eligibility)	X	X							X								X	X
Stool (metagenomics) (Screening samples will not be evaluated for eligibility)	X	X				X			X								X	X
Stool (metabolomics) (Screening samples will not be evaluated for eligibility)	X	X							X								X	X
Stool (microbiology)	X	X							X								X	X
Fecal pH (using nitrazine paper)	X	X							X								X	X

Statistical Analysis Plan

Prolacta Bioscience Protocol 20-CT-001

Protocol Number 20-CT-001																
Schedule of Events For Cohort 5 (Day 0 through Day 22)																
Events	Cohort 5 Screening	Cohort 5 1 st Dosing Course														Cohort 5 1 st Washout
	D0 (≤ 90 days prior to D1)	D1	D2	D3	D4	D5 (+1D)	D6	D7	D8 (+2D)	D9	D10	D11	D12	D13	D14	D15 (+2D)
Urine Drug Screen Test	X															
Urine Pregnancy Test (Females of child-bearing potential)	X															
Hematology & Chemistry testing	X	X														X
Immunology testing (Screening samples will not be evaluated for eligibility)	X	X							X							X
Stool (metagenomics) (Screening samples will not be evaluated for eligibility)	X	X				X			X							X
Stool (metabolomics) (Screening samples will not be evaluated for eligibility)	X	X							X							X
Stool (microbiology)	X	X							X							X
Fecal pH (using nitrazine paper)	X	X							X							X

Cohort 5 (cont.)

Statistical Analysis Plan

Prolacta Bioscience Protocol 20-CT-001

Protocol Number 20-CT-001																	
Events	Schedule of Events For Cohorts 5 Only (Day 29 through Day 57)															Cohort 5 2 nd Dosing Course	
	D29	D30	D31	D32	D33 (+1D)	D34	D35	D36 (+2D)	D37	D38	D39	D40	D41	D42	D43 (+2D)	D50 (+2D)	D57 (+2D)
Clinic visit	X							X							X		X
Final Visit																	X
Physical Exam																	X
Vital Signs (Temp, BP, pulse, RR)	X							X							X		X
Prior & Con Meds	X							X							X		X
AEs	X							X							X		X
Dispense IP: PPI(if applicable) ¹ , B. infantis ($\geq 8 \times 10^7$ cfu/d) (Note: On D29 dispense 9-day supply of PBCLN-005. On D36 dispense 5-day supply of PBCLN-005)		X ¹							X ¹								
Dosing: PPI ¹	X ¹	X ¹	X ¹	X ¹	X ¹	X ¹	X ¹										
Dosing: B. infantis ($\geq 8 \times 10^7$ cfu/d)	X	X	X	X	X	X	X										
Dosing: PBCLN-005 (Target 18g)	X	X	X	X	X	X	X	X	X	X	X	X	X	X			

Cohort 5 (cont.)

Statistical Analysis Plan

Prolacta Bioscience Protocol 20-CT-001

Protocol Number 20-CT-001																		
Events	Schedule of Events For Cohorts 5 (Day 29 through Day 57)																Cohort 5 Only Washout	
	Cohort 5 2 nd Dosing Days																	
	D29	D30	D31	D32	D33 (+1D)	D34	D35	D36 (+2D)	D37	D38	D39	D40	D41	D42	D43 (+2D)	D50 (+2D)	D57 (+2D)	
Assess IP and Stool compliance	X							X								X		X
Stool Questionnaire	X	X	X	X	X	X	X	X	X	X	X	X	X	X	X	X	X	
Daily Dosing and Flavor Questionnaire	X	X	X	X	X	X	X	X	X	X	X	X	X	X				
Patient Phone Calls	X	X	X	X	X	X	X	X	X	X	X	X	X	X				
Hematology & Chemistry testing	X															X		X
Immunology testing	X							X								X		X
Stool (metagenomics)	X				X			X								X	X	X
Stool (metabolomics)	X							X								X		X
Stool (microbiology)	X							X								X		X
Fecal pH (using nitrazine paper)	X							X								X		X

4.5 SAMPLE SIZE

Six groups of 10 subjects will be included in this study for a total sample size of 60. The sample size was not determined statistically, but rather represents a typical number for an exploratory study of healthy volunteers.

4.6 TIMING OF ANALYSES

There will be a single analysis of the data at the conclusion of the enrolment of the subjects and the collection of the study endpoints

4.7 ANALYSIS POPULATIONS

Since this study is a safety study, the only analytical population will be individuals who receive at least one dose of either active drug or placebo.

4.8 MISSING DATA

Investigators should make every effort to ensure that loss to follow-up is kept to a minimum and that all data are collected for all subjects at all time points. However, because this is a Phase 1 safety study, no data imputation methods will be used to account for missing data.

4.9 INTERIM ANALYSES AND DATA MONITORING

There are no interim analyses conducted during this study.

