An unconcentrated, pasteurized form of HMO material containing a proportional amount of lactose has already been used in an NIH sponsored clinical trial in premature infants with no reported ill effects.^v Prolacta Bioscience has also completed a healthy volunteer study using the same HMO material as in this trial (with no addition of *B. infantis*) which showed good tolerability. No treatment emergent adverse effects were reported over the course of the trial.^{vi}

The *B. infantis* preparation being used in this trial is a dietary supplement commercially available in the United States and marketed for use in infants. *B. infantis* is characterized as “generally regarded as safe” (GRAS).⁸

Hypothesis

The primary goal of this study is to evaluate the synergy of PBCLN-005 in varying doses with a fixed dose of *B. infantis*, compared with either component of the IP given alone. Synergy is defined as the enhanced gastrointestinal colonization of *B. infantis* upon feeding with HMO feeding. Secondary endpoints will measure changes in the gut microbiome, fecal metabolome and the subject’s immune status as measured by systemic markers. We hypothesize that the combination will result in greater proliferation of *B. infantis* than was seen with the HMO concentrate alone.

Another objective is to understand the role of the low pH of the stomach in colonization of *B. infantis*. For most non-spore forming gut bacteria, the stomach is a barrier to colonization since acid exposure can reduce bacterial titer by 1,000- to 1,000,000-fold. While some subjects in the study will take a proton pump inhibitor (PPI; Zegerid), or a proton pump inhibitor (Zegerid) and

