histamine H2-receptor antagonist (H2 blocker: Pepcid) to transiently reduce the production of gastric acid prior to *B. infantis* ingestion, some study groups will ingest *B. infantis* without PPI pretreatment. It was initially hypothesized that PPI might be necessary to observe *B. infantis* colonization distal to the acid milieu of the stomach. Preliminary data from the first group of subjects tested suggest that omeprazole may be inhibitory to *B. infantis* colonization and that colonization occurs in the absence of gastric acid suppression. *In vitro* data suggest that the inhibitory effect is not seen with the histamine H2-receptor antagonist famotidine. Therefore, this has resulted in a change to this hypothesis. We now seek to determine if colonization occurs in the presence of an acidic milieu in the stomach, if the apparent inhibitory effect of PPI on colonization is real and if the prediction that the effect will not be seen with famotidine is correct because all target group subjects for future studies are on acid blockers.

We also hypothesize that ingestion of PBCLN-005 along with the *B. infantis* will result in a more marked change in immune markers than was seen in the previous study in healthy adults. We will, therefore, evaluate changes in circulating cytokine and growth factor levels following the ingestion of the IP compared to baseline levels and between dose groups.

Methods

We propose to conduct an unblinded six cohort multi-dose trial using 10 subjects per cohort for a total of 60 healthy adult volunteers ages 18-44 in order to evaluate the effects of the use of HMO Concentrate (PBCLN-005) and *B. infantis* on the human microbiome.

Six separate cohorts of both male and female study subjects will receive some form of the IP. All subjects in Cohort groups 1-4 and 6 will be followed from the day of the first dose of IP (day 1) until 28 days (day 29) after the first dose. Subjects in Cohort 1 will consume *B. infantis* once per day for 7 days. Subjects in Cohort 2-4 and Cohort 6 will consume the IP twice per day for 14 consecutive days. Cohorts 1-4 and Cohort 6 will be followed until the 28th day (day 29) following the first day of the feeding protocol (day 1).

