10 CHANGES IN CONDUCT OF STUDY OR TO PLANNED ANALYSES FROM PROTOCOL

Deviations from the statistical analyses outlined in this plan will be indicated; any further modifications would be noted in the final statistical analysis.

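### The SAP's acid-blocker exposure conflicts with the protocol for 40 of 60 planned subjects and with its own schedules, and the SAP does not record the early-data review that changed the PPI hypothesis

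*Combined protocol and SAP*

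**What the plan says.** **Timing and record.** SAP 4.6 states: "There will be a single analysis of the data at the conclusion of the enrolment of the subjects", once the endpoints are also collected. SAP 4.9 adds: "There are no interim analyses conducted during this study". SAP 10, where changes from the protocol belong, gives only a general undertaking: "Deviations from the statistical analyses outlined in this plan will be indicated".

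**Early data.** The protocol's Hypothesis section says that a PPI was at first thought possibly necessary for colonization. It continues: "Preliminary data from the first group of subjects tested suggest that omeprazole may be inhibitory to" *B. infantis* colonization, and in vitro "data suggest that the inhibitory effect is not seen with the histamine H2-receptor antagonist famotidine". The consequence is explicit: "Therefore, this has resulted in a change to this hypothesis". One question is now "if the apparent inhibitory effect of PPI on colonization is real".

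**Exposure.** The protocol's Hypothesis section says "While some subjects in the study will take a proton pump inhibitor", or a PPI and an H2 blocker, and that other groups take *B. infantis* without PPI pretreatment. Protocol Table 1 confines PPI to Cohort 5, first course. In that cohort's second course, four subjects take an H2 blocker and four take no acid blocker. Two further Cohort 5 subjects had been dosed before Protocol Revision 4.

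The SAP section on the purpose of the analyses says instead that the majority of subjects receive PPI and one group does not, and it hypothesizes that colonization requires PPI. SAP Table 1 (section 4.1) lists PPI for Cohorts 1 to 5. The SAP 4.4 schedule for the second course of Cohort 5 lists PPI, where applicable, and no H2 blocker. SAP 5 gives every summary table one column per cohort.

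**The concern.** The study now asks whether PPI hinders colonization, and the protocol explains that the target subjects of future studies take acid blockers. Even a descriptive answer needs to show correctly who took which acid blocker. An analyst working from the SAP would start from the opposite hypothesis and from an exposure table that differs from the protocol in four of six cohorts. In the second course of Cohort 5, the planned table layout would put subjects with different acid-blocker exposure in one column.

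A reader of the SAP alone would also believe that no outcome data were examined before the end. That reader could not tell which subjects prompted the PPI question and which provide new evidence on it.

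**Working it through.** **1. The plan's own total.** SAP 4.5 and the protocol's Sample Size section give six groups of 10: 6 × 10 = 60, which reproduces. The size was not determined statistically, so there is no alpha or power figure to check.

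**2. PPI on days 1 to 7, by source.**

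| Cohort | Planned n | SAP Table 1 | SAP 4.4 schedule | Protocol Table 1 |
|---|---|---|---|---|
| 1 | 10 | Yes | no PPI row | No |
| 2 | 10 | Yes | no PPI row | No |
| 3 | 10 | Yes | no PPI row | No |
| 4 | 10 | Yes | no PPI row | No |
| 5 (course 1) | 10 | Yes | dosing rows not in the text available | Yes |
| 6 | 10 | No | no PPI row | No |

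- SAP Table 1: 5 × 10 = 50 of 60 on PPI.
- Protocol Table 1: 1 × 10 = 10 of 60 on PPI.
- Labels differ in Cohorts 1 to 4: 4 × 10 = 40 of 60 (66.7%).
- Among the 5 × 10 = 50 planned *B. infantis* recipients (all cohorts except 2), labels differ in Cohorts 1, 3 and 4: 3 × 10 = 30.
- SAP Table 1 disagrees with the SAP's own schedules in the same four cohorts.

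**3. Second course of Cohort 5.** The protocol's numbers add up: 2 dosed before Revision 4 + 4 with H2 blocker + 4 with no acid blocker = 10. The protocol does not state which acid blocker, if any, the first two took in a second course. The SAP schedule shows PPI with a conditional qualifier; the text of its footnote is not in the material available. A single Cohort 5 column therefore holds at least two exposure groups, and possibly three.

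**4. The record of the review, side by side.**

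- Protocol: early colonization data plus in vitro data led to a changed hypothesis, and the Cohort 5 scheme was revised after two subjects had been dosed.
- SAP 4.6, 4.9 and 10: one analysis, no interim analyses, no specific change recorded.

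The protocol does not say outright that the first group of subjects belonged to this trial. It is very likely: the sponsor's completed volunteer study gave no *B. infantis*, and the Revision 4 note describes subjects of this trial who had already been dosed. The protocol does not say which subjects were reviewed, in which cohorts, or when.

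**5. What is not affected.** Cohort 5 first course against Cohort 6 is the PPI comparison at a matched HMO dose (18 g in both). Both Table 1s label it the same way: PPI in Cohort 5, none in Cohort 6.

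**The case against.** The strongest reply is that this is version control. The SAP gives ages 18-75 against 18-44 in the protocol, so it seems to follow an older protocol version, and 4.6 and 4.9 may have been accurate when written. SAP 2 limits this version to an abbreviated safety report and promises an amended SAP for the endpoints. The protocol itself discloses the changed hypothesis. The trial is unblinded and descriptive, and the protocol never calls the review an interim analysis.

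Much of this stands. It explains the mismatch and rules out a charge of concealment. The deferral also means that the empty section 7.4 on PPI is no fault here. But SAP 2 defers endpoint detail; it does not defer the exposure table, the statement on interim analyses or the section on changes. This version governs the safety report, which summarizes exposure and adverse events by dose group.

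Three stronger readings are tempting, and the documents do not support them.

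- A reader might infer that a hidden interim analysis inflated the type I error. No hypothesis test, alpha or stopping rule is described, so there is no error rate to inflate.
- A reader might infer that a pooled PPI effect will be diluted or biased by a calculable amount. No pooled PPI contrast is planned, and one would mix HMO doses of 0, 4.5, 9 and 18 g. A wrong label leaves the values in a cohort's column unchanged. Any bias from including the reviewed subjects cannot be sized without knowing who they were.
- A reader might infer that 40 subjects actually received something other than planned. The 40 counts planned labels only; actual PPI exposure in Cohorts 1 to 4 is not stated.

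**Conclusion.** The concern holds as a conflict between documents and a gap in the record. SAP and protocol disagree on PPI for 40 of 60 planned subjects, the SAP disagrees with its own schedules for the same four cohorts, and its hypothesis is the one the protocol has replaced. The planned layout would also merge Cohort 5 second-course subjects with different acid-blocker exposure. This part changes reported results, and correcting a label alone would not resolve it. The SAP has no record that early colonization data contributed to the change.

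The count rests on planned cohort sizes and on the two Table 1s as printed. That the early data came from this trial is a strong inference. No effect on an estimate is claimed, and the labels for Cohort 5 first course against Cohort 6 are sound. The point should be addressed before the amended SAP is final and, for the exposure table, before the safety report.

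**What to change.** 1. **Reconcile.** Bring the SAP purpose section, SAP Table 1, the SAP 4.4 schedules for Cohorts 1 to 4 and the second course of Cohort 5 into agreement with one another and with the protocol's Hypothesis section, Table 1 and Cohort 5 schedule. This review takes no view on which regimen is right.
2. **Summarize by exposure received.** Add a subject-level flag for acid-blocker exposure actually received. Show Cohort 5 second-course results separately for the H2-blocker and no-blocker subjects, and list the two pre-Revision 4 subjects individually.
3. **Record the review.** In SAP 4.9 or 10, state which early data were examined, from which subjects, when, and what changed. Flag those subjects. A display restricted to later subjects may be added beside the full one as an optional sensitivity display; it should not replace it.

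**Cost.** Wording, two flags and minor extra programming. Cells become small: for a within-subject comparison at n = 4, the 95% half-width is t(0.975, 3)/√4 = 3.182/2 = 1.59 SD of the paired difference, so those displays are supportive only and need a note on order and carry-over. The optional display also loses precision. If the two early Cohort 5 subjects were the ones reviewed (an assumption), the half-width for Cohort 5 against Cohort 6 goes from 2.101 × √(1/10 + 1/10) = 0.94 SD to 2.120 × √(1/8 + 1/10) = 1.01 SD, about 7% wider.
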